1.1 Name, Description and Intended Use of the Test and Control Articles (Treatments)

The single investigational test article, ZuraPrep™
is being evaluated for efficacy as a
preoperative skin preparation solution by demonstrating its immediate and persistent antimicrobial properties. Testing will be performed based upon procedures outlined in the FDA Safety and Effectiveness of Health Care Antiseptics; Topical Antimicrobial Drug Products for Over-the-Counter Human Use, Final Rule (Federal Register Volume 82, Number 243, Wednesday, December 20, 2017) and ASTM E1173 – 15 Evaluation of Preoperative, Precatheterization, or Preinjection Skin Preparations.
ZuraPrep™ Solution Vehicle, will be evaluated as a negative control (ZuraPrep™
ChloraPrep® will be evaluated as an active control (reference control).

1.2 Risk/Benefit Summary

There are minimal anticipated adverse health risks for the participants of this study. Considerable safety and efficacy data are available for the active ingredient in the test and control formulations as described in the investigator brochure (IB).

1.3 Treatment Application Configurations

This study treatment will	be conducted using ZuraPr	ep™ Proposition of the second
, ZuraPrep™	Vehicle,	and ChloraPrep®,
. The pro	duct (including packaging) wi	Il be weighed pre-application
and post-application.		

The treatments will be applied topically to intact skin of the abdomen and groin regions of each subject. The treatments will be applied per the Treatment Application Instructions (Appendix 14.7).

1.4 Good Clinical Practice and Regulatory Requirements

This study will be conducted in compliance with this protocol, Good Clinical Practice (GCP) including 45 CFR 160 and 164 (Authorization for Use/Disclosure of Protected Health Information (PHI), 21 CFR 50 (Protection of Human Subjects), 56 (Institutional Review Boards), 330 (Over-The-Counter Human Drugs which are generally recognized as safe and effective and not misbranded) and Tentative Final Monograph for Health Care Antiseptic Drug Products (TFM), International Conference on

Page 6 of 53 Zurex Pharma, Inc. Project: ZX-ZP-0092 Microbac Protocol: 865.1.03.25.18

Microbac Project: 865-107

Harmonisation ICH Harmonised Tripartite Guideline E6: Good Clinical Practice, the Standard Operating Procedures of Microbac, the study protocol and any protocol amendments.

1.5 Study Population

Healthy male and female volunteers, 18 years of age or older, with no dermatological conditions or known history of sensitivity to natural rubber latex, adhesive skin products (e.g., Band-Aids, medical tapes), isopropyl alcohol or chlorhexidine gluconate will be enrolled into this study. For this trial, a sufficient number of volunteers will be recruited in the screening phase such that a total of at least 72 abdominal (sebaceous poor) regions and 72 groin (sebaceous rich) regions are evaluable at the completion of the study for each treatment. Subjects must satisfy all Screening Day and Treatment Day Inclusion/Exclusion Criteria prior to screening sample collection and Treatment Day procedures.

[figure not shown]
The right and left sides of both the abdomen and the groin must meet the minimum Screening Day baseline values stated in the Inclusion Criteria (Section 4.1) to qualify for the study.

At least 108 human subjects will be employed utilizing bilateral applications assuring that the treatments will be evaluated on the sites as described in the following table:

Table 1.5: Minimum number of readings per anatomical site (abdomen and groin), per treatment, per sampling interval (30 seconds and 6 hours post-application)

Treatment	Number of Abdomen Evaluations	Number of Groin Evaluations
ZuraPrep™	72	72
ChloraPrep® (active control)	72	72
ZuraPrep™ Vehicle, (negative control)	72	72

2. Study Objectives and Purpose

The secondary objective of this study is to show persistent effect as defined in the Health Care Antiseptics, Topical Antimicrobial Drug Products Final Rule of December 20, 2017, Microbac - Confidential

Page 7 of 53 Zurex Pharma, Inc. Project: ZX-ZP-0092 Microbac Protocol: 865.1.03.25.18

Microbac Project: 865-107

(Final Rule). Due to the normal variability associated with this biological system, the test article is considered to have persistent effect if the percentage of body sites with \log_{10} CFU/cm² values less than or equal to baseline for the 6-hour sample is between 95 to 100%.

3. Study Design

3.1 Study Type

This is a randomized, paired-comparisons design where each subject receives two of the planned treatments.

 Table 3.1:
 Treatments, Anatomical Sites of Evaluation, Application and Dry Times and Coverage

Areas (See Appendix 14.7 for detailed application instructions)

Treatment (Quantity/Volume)	Body Site	Application Time	Dry Time	Area of Coverage
ZuraPrep™	Abdomen (sebaceous poor)	30 seconds	3 minutes	5" x 5"
	Groin (sebaceous rich)	2 minutes	3 minutes	1.5" x 5"
ChloraPrep®	Abdomen (sebaceous poor)	30 seconds	3 minutes	5" x 5"
(active control)	Groin (sebaceous rich)	2 minutes	3 minutes	1.5" x 5"
ZuraPrep™ Vehicle,	Abdomen (sebaceous poor)	30seconds	3 minutes	5" x 5"
(negative control)	Groin (sebaceous rich)	2 minutes	3 minutes	1.5" x 5"

3.2 Primary Endpoint/Analysis

The primary analysis for the study utilizes the standards of the Health Care Antiseptics, Topical Antimicrobial Drug Products Final Rule of December 20, 2017. The primary efficacy criteria will be assessed based on log₁₀ CFU/cm² values at 30 seconds for immediate effect and at 6 hours for persistent effect.

Product effectiveness will be measured using superiority and non-inferiority estimates for the 30-second sample time calculated using average treatment effects (ATEs). ATEs will be estimated from a linear regression of the 30 second post-treatment bacterial counts (log₁₀ scale) on the additive effect of a treatment indicator and the baseline or pre-treatment measurements (log₁₀ scale). To show effectiveness the test product will be (1) non-inferior to ChloraPrep® with a 0.5 margin (upper bound of 95% confidence interval of the ATE of the test product versus active control value < 0.5) and (2) superior to the ZuraPrep Vehicle (negative control) by a margin of 1.2 (lower bound of the 95% confidence interval of the ATE of the test product versus

Page 8 of 53 Zurex Pharma, Inc. Project: ZX-ZP-0092 Microbac Protocol: 865.1.03.25.18

Microbac Project: 865-107

the vehicle value > 1.2). Superiority and non-inferiority will be calculated separately for each body area (abdomen and groin).

A site is considered evaluable for efficacy (part of the per-protocol data set) if the criteria in the following table are met:

Table 3.2: Minimum and Maximum Treatment Day Baseline Values per Anatomical Site

Anatomical Site	Minimum and Maximum Treatment Day Baseline*
Abdomen	1.0 x 10 ³ – 3.2 x 10 ⁵ CFU/cm ² (3.0 Log ₁₀ – 5.5 Log ₁₀)
Groin	1.0 x 10 ⁵ - 3.2 x 10 ⁷ CFU/cm ² (5.0 Log ₁₀ - 7.5 Log ₁₀)

^{*}Note: For the Screening Day baseline, the maximum upper limit does not apply. Only the minimum criteria must be met.

3.2.1 Secondary Endpoints/Analysis

Persistence or long-term efficacy is defined in the Final Rule as having the 6 hour post-treatment log₁₀ CFU/cm² values lower than or equal to the baseline log₁₀ CFU/cm² values for 100 percent of the subjects in each indication and body area. Due to the normal variability associated with this biological system, the test article is considered to have persistent effect if the percentage of body sites with log₁₀ CFU/cm² values less than or equal to baseline for the 6-hour sample is between 95 to 100%. All subjects that do not achieve the 6-hour efficacy goal will be documented and discussed. This only applies to ZuraPrep™ for the purpose of determining efficacy but the same calculation will be performed for ChloraPrep® for information purposes only.

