3.10 Computerized System

•

Page 16 of 53 Zurex Pharma, Inc. Project: ZX-ZP-0092 Microbac Protocol: 865.1.03.25.18

Microbac Project: 865-107

4. Subject Selection

Healthy volunteers with no dermatological conditions or known history of sensitivity to natural rubber latex, adhesive skin products (e.g., Band-Aids, medical tapes), isopropyl alcohol, citric acid, methylparaben, propylparaben, or chlorhexidine gluconate will be enrolled into this study. A sufficient number of volunteers will be enrolled in the screening phase such that the total number of abdominal regions and the total number of groin regions meets or exceeds the number determined for the study (72 abdominal regions and 72 groin regions for each treatment). Subjects must satisfy all Screening Day and Treatment Day Inclusion/Exclusion Criteria prior to screening sample collection and Treatment Day procedures. Volunteers will be recruited and treated until the count of results in the per protocol data set meets or exceeds the required test material/region counts.

A subject must qualify for both the abdominal portion and the groin portion of the study and the right and left sides of the abdomen and groin must meet the minimum baseline values stated in the Inclusion Criteria in order to be eligible for Treatment Day procedures.

Sites which are treated but discovered to have Treatment Day baseline counts below the minimum values or above the maximum values stated in Table 3.2 will not be included in the primary efficacy analysis (per-protocol data set). Additional subjects will be recruited and treated identically to the treatments for the subjects who had non-qualifying sites until a sufficient number of qualifying sites have been treated.

Subjects will be identified at screening by their initials and a screening ID number. Subject numbers will not be assigned until a subject has passed the screening criteria, including baseline bacterial counts.

All volunteers will be given verbal and written information about the study procedures, and Subject Instructions (Appendix 14.6) will be provided to each subject for the pre-treatment phase of the study. The following Inclusion/Exclusion Criteria will be reviewed on Screening Day and on Treatment Day to establish eligibility for participation:

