8.1 Data Sets Analyzed

The Intent-to-Treat (ITT) population will consist of all subjects who pass the pre-test period prior to baseline screening and are assigned a subject number for treatment. The ITT data set will include data for all of the ITT population. The ITT data set will be used for the safety analysis.

[figure not shown]
Since each body site (left or right for abdomen or groin) can pass or fail Treatment Day baseline requirements separately, the per-protocol data set will be defined as those sites passing treatment day baselines on a site-by-site basis. Subjects are therefore included in the per-protocol population if and only if they have at least one qualifying body site. The per-protocol data set will be evaluated for efficacy.

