8.2 Statistical Methods

8.2.1 Efficacy Analyses

CFU values will be calculated as per the Bacterial Enumeration methods above. Individual plate CFU counts that are zero will be treated as 0.5 for further calculations.

Product effectiveness will be measured using superiority and non-inferiority estimates for the 30-second sample time calculated using average treatment effects (ATEs). ATEs will be estimated from a linear regression of the 30 second post-treatment bacterial counts (\log_{10} scale) on the additive effect of a treatment indicator and the baseline or pre-treatment measurements (\log_{10} scale). Superiority and non-inferiority will be estimated as follows:

Superiority and non-inferiority will be calculated separately for each body area.

Persistence or long-term efficacy is defined as having the 6 hours post-

Page 30 of 53 Zurex Pharma, Inc. Project: ZX-ZP-0092 Microbac Protocol: 865.1.03.25.18

Microbac Project: 865-107

treatment log₁₀ CFU/cm² values lower than or equal to the baseline log₁₀ CFU/cm² values for 100% of the subjects in each body area. Due to the normal variability associated with this biological system, the test article is considered to have persistent effect if the percentage of body sites with log₁₀ CFU/cm² values less than or equal to baseline for the 6-hour sample is between 95 to 100%. All subjects that do not achieve the 6-hour efficacy goal will be documented and discussed.

The efficacy calculations (superiority and persistence) only apply to ZuraPrep $^{\text{TM}}$ for the purpose of determining efficacy, but the same calculations will be performed for ChloraPrep $^{\text{R}}$ for information purposes only.

Summary statistics for the log₁₀ CFU/cm² values at each time point and the respective changes from baseline will be calculated, grouped by time point, test product, and body area. These statistics are for information purposes only and are not part of efficacy calculations.

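### One Treatment Day count both admits a site to the efficacy set and sets the bar its 6-hour count must stay under, so the persistence percentage is open to regression-to-the-mean bias, probably but not certainly upward

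*Combined protocol and SAP*

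**What the plan says.** **The success rule.** Sections 3.2.1, 6.1.1 and 8.2.1 count a site as persistent if its 6-hour log10 count does not exceed its baseline. In Section 3.2.1, "the test article is considered to have persistent effect if the percentage of body sites with" such a result reaches the required range. Section 8.2.1 gives the same range: the product succeeds if the percentage of sites "less than or equal to baseline for the 6-hour sample is between 95 to 100" per cent. The plan attributes the at-or-below-baseline definition to the Final Rule and relaxes that rule's 100% to 95%.

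**Who is counted.** Section 3.2 states: "A site is considered evaluable for efficacy (part of the per-protocol data set) if the criteria in the following table are met". Table 3.2 gives 3.0 to 5.5 log10 CFU/cm² for the abdomen and 5.0 to 7.5 for the groin. Section 4 (Subject Selection) says that sites with "Treatment Day baseline counts below the minimum values or above the maximum values stated in Table 3.2 will not be included"; the exclusion is from the primary efficacy analysis, and further subjects are treated to replace them. Section 8.1 confirms that "the per-protocol data set will be defined as those sites passing treatment day baselines on a site-by-site basis", and adds: "The per-protocol data set will be evaluated for efficacy". Of the other set it says: "The ITT data set will be used for the safety analysis". No persistence percentage outside the per-protocol set is planned.

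**How baseline is measured.** Each test area has one baseline sampling site and one for each post-treatment time (5.1.2.1.1, 5.1.2.1.2). The persistence text does not say which baseline it means, but Section 6.1 measures reduction from the Treatment Day baseline. Subjects must also have met the same minima, left and right, on an earlier Screening Day, when no maximum applies (4.1 and the note to Table 3.2).

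**The concern.** A single scrub-cup count carries sampling error. When that count must clear a floor before the site is analysed, sites with a negative error are lost more often than sites with a positive one, so the retained baselines are on average too high. A 6-hour count with fresh error then falls below them more easily. The ceiling works in the opposite direction.

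The Screening Day floor does not cause this, because its error is separate from the Treatment Day error. Nor does it prevent it. The 30-second regression includes baseline as a covariate, so this point does not extend to it. The persistence percentage is a raw comparison of each site with its own baseline and has no such adjustment.

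At stake is a yes-or-no conclusion at a fixed 95% cut. Where the true percentage is just under that cut, a few points of bias change the chance of declaring persistence considerably.

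**Working it through.** **Inputs from the plan**
- Denominator: 108 subjects × 2 treatments each ÷ 3 treatments = 72 sites per treatment and body area, which reproduces Table 1.5.
- Pass rule: 68/72 = 94.4% fails and 69/72 = 95.8% passes, so at least 69 successes are needed.
- Band width in Table 3.2: 5.5 − 3.0 = 2.5 and 7.5 − 5.0 = 2.5 log10.

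**Assumptions (not in the readable documents)**
- True site levels are normal with SD 0.6 log10. Screening, Treatment Day and 6-hour errors are independent with SD 0.5.
- The true 6-hour reduction d is 1.0 log10.
- The population mean lies 0 to 2.0 log10 above the floor.
- The 72 sites are independent, which is reasonable because each subject contributes one ZuraPrep site per body area.

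**Step 1: rate without Treatment Day selection.** The rate is Φ(d ÷ (SD × √2)) = Φ(1.0 ÷ (0.5 × 1.414)) = Φ(1.414) = 92.1%. The chance of passing is the binomial probability of at least 69 of 72 at that rate, which is 0.17.

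**Step 2: rate with the Table 3.2 band.** This was simulated. A site needs a screening count at or above the floor and a Treatment Day count between the floor and the floor + 2.5. It succeeds if its 6-hour count does not exceed its Treatment Day count.

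| Mean above floor (log10) | Rate, unselected | Rate, per-protocol | Chance of ≥69/72, unselected | Chance, per-protocol |
|---|---|---|---|---|
| 0 | 92.1% | 96.5% | 0.17 | 0.76 |
| 0.5 | 92.1% | 95.1% | 0.17 | 0.52 |
| 1.0 | 92.1% | 93.5% | 0.17 | 0.31 |
| 1.5 | 92.1% | 92.0% | 0.17 | 0.16 |
| 2.0 | 92.1% | 90.1% | 0.17 | 0.07 |

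Repeat runs move the rates by about 0.1 point and the chances by about 0.01.

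**Step 3: floor and ceiling separately.** With between-site SD 0.5 and the mean 1.5 above the floor, the floor alone moves 92.1% to 92.7%. Adding the ceiling brings it back to 92.1%.

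**Step 4: where it does not matter**
- No true effect: 50% unselected. Over within-site SDs 0.3 to 0.7 and between-site SDs 0.5 to 0.8, the band gives 58–66% with the mean at the floor and 46–49% with the mean 1.5 above. The chance of 69 of 72 is essentially zero throughout.
- Larger effect: at d = 1.5 and within-site SD 0.5, Φ(1.5 ÷ 0.707) = 98.3%, and the pass chance is already 0.97 without selection.
- Less error: at within-site SD 0.3 and d of at least 1.0, the rate changes by under 1 point.

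**Step 5: likely direction.** Appendix 14.10 puts normal skin flora generally at 10² to 10⁵ CFU/cm², depending on body site. The groin floor of 10⁵ is at the top of that range and the abdominal floor of 10³ is inside it. That suggests means near the floor, where the bias is upward.

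**The case against.** **The ceiling.** A reader might infer that the percentage is simply inflated. The documents do not support that. Table 3.2 has a maximum as well as a minimum, and the sign turns when the mean is about 1.5 log10 above the floor. The flora range in Appendix 14.10 is a general background statement, not data from qualified subjects, so it makes upward bias likelier without establishing it. This objection stands in full.

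**The size is assumed.** Two modelling choices favour a larger effect.
- Screening was modelled per site, whereas the plan requires both sides to qualify. With an assumed left-right correlation of 0.7 and the mean at the floor, a pass chance of about 0.75 falls to 0.68.
- Baseline and 6-hour samples are taken on the same day, so some error may be shared and cancel. If half the error variance were shared, the unselected rate would be Φ(1.0 ÷ (0.354 × 1.414)) = Φ(2) = 97.7%. The pass chance would be about 0.92 without selection and 0.95 to 0.99 with it, for means up to 1.0 above the floor.

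Both points shrink the effect; neither removes the mechanism.

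**No minimum change.** A reader might also fault the plan for accepting any value at or below baseline. The plan takes that definition from the Final Rule and requires every failure to be documented and discussed, so it is not an error here.

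**Evaluability is deliberate.** The plan restricts efficacy to sites in a stated range, and persistence is headed as secondary, although Section 3.2 also names 6 hours under the primary efficacy criteria. This is a fair reason not to replace the deciding set. It is no reason to omit an unselected figure.

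**Conclusion.** The point holds as a conditional bias. Selection and threshold share one error-prone count, the percentage is unadjusted, and no unselected figure is planned.

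Under the stated assumptions at a true 1.0 log10 reduction, selection moves the rate by between +4.4 points (96.5 − 92.1) and −2.0 points (90.1 − 92.1). The sign and size in this trial cannot be settled from the documents; upward is the likelier direction. The problem is confined to products near the 95% cut. The stronger inference, that regression to the mean could carry an inactive product past the rule, is not supported: such a product fails in every scenario examined. Products with reductions well above 1 log10 are little affected.

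The gap is worth closing before the data are seen, but it does not undermine the 30-second comparisons.

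**What to change.** In Sections 3.2.1, 6.1.1 and 8.2.1, add wording to this effect:

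*The 6-hour percentage will also be calculated for each body area over all treated ZuraPrep sites that have a Treatment Day baseline and a 6-hour count, without applying the Table 3.2 range. It will be reported beside the per-protocol percentage. If the per-protocol percentage is at least 95% and the all-treated percentage is below 95%, the persistence conclusion will be described as sensitive to baseline selection.*

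This removes the Treatment Day selection whichever way it runs. The per-protocol criterion and the 30-second analysis stay as they are.

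The cost is wording and one extra percentage per body area. No new sampling is needed: plates incubate for 72 ± 4 hours (5.2.3), so the 6-hour sample is taken before anyone knows whether the baseline qualified, and Appendix 14.2 lists the baseline count after sampling. The downside is that the companion figure may be slightly less favourable and includes sites outside the plan's evaluability range, which the report should say.

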3.2.2 Study Validity

There are no study validity criteria. All calculations performed for ZuraPrep™ will be performed for ChloraPrep® , but for informational purposes only.

3.3 Randomization and Blinding

Subjects will be randomized before treatment, after screening eligibility is determined. Subjects will be randomized to treatment using the following block design:

Treatment Balance

Each subject will receive two different treatments, one on the right side of the body and one on the left.

The treatment assignments will be balanced such that the number of readings per anatomical site matches the calculated requirements.

Page 9 of 53 Zurex Pharma, Inc. Project: ZX-ZP-0092 Microbac Protocol: 865.1.03.25.18

Microbac Project: 865-107

Left/Right Balance

The application will be randomized so that each treatment is used on an equal number of left and right sides of the body.

Site and Sample Time Balance

Within each anatomical site, sample order with respect to sampling area number will be balanced with respect to treatments.

The randomization plan is based on the estimated population size

Subjects will be randomized to treatments in blocks of 12, randomly ordered within the block. Sample order will be randomized separately in blocks of 24 based on the 24 possible sample orders; 12 of the sample orders will be matched to the 12 treatment assignments in such a way to balance treatment with respect to sample order. Additional details on the randomization will be found in the randomization document.

The Investigator is responsible for ensuring that the randomization is followed. A basic outline of a randomization schedule for the abdominal and groin sites is provided in Appendix 14.4. The final randomization schedule will be prepared before the initial treatment. The test and control articles will be labeled with the appropriate codes as designated by the study randomization.

Subjects will be identified by their initials, a Screening ID Number, and a Subject Number. Subject Numbers will not be assigned until a subject has passed the screening criteria, including baseline bacterial counts (at least 1.0×10^5 CFU/cm² in the groin and at least 1.0×10^3 CFU/cm² on the abdomen). Subjects whose abdominal and groin regions qualify will be assigned the Subject Number on Treatment Day. Therefore, each of the participating treated subjects will be assigned two identification numbers: Screening Identification Number and a Subject Number.

- Screening subjects will be assigned numbers ranging from 9001 to 9999.
- Subjects to be treated (including treatment day baseline collection) will be assigned sequential numbers ranging from 1001 up to the total number of test subjects treated.

The study materials will not be blinded from the Investigator or other study staff performing the study material application or bacterial sample collections. The staff member(s) performing bacterial enumeration will be blinded from the identification of treatment assignment. The study staff performing the bacterial enumeration will not be involved in the study material application or the collection of samples. The Raw Data Capture form sections will be maintained separately (from the pages which include study treatment identifications) during the conduct phase of the study. The study staff performing the bacterial enumeration will record counts directly onto the Raw Data Capture forms without accessing the subject study documentation folder containing the other source document pages. The Raw Data Capture forms will be compiled with

Page 10 of 53 Zurex Pharma, Inc. Project: ZX-ZP-0092 Microbac Protocol: 865.1.03.25.18 Microbac Project: 865-107

the entire subject source record after all data recording has been completed. The data capture forms will serve as the source document.

Data will first be recorded onto the data capture forms, followed by entry into the electronic Case Report Form (eCRF). Wherever the data are entered first is considered the source document.

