5.1.2.1.1 Preparation of Abdominal Test Area

The test site within the abdominal region (abdominal test area) is defined as the area below the umbilicus and above the groin. Using a 5" x 5" sterile template, the corners of each abdominal test area will be marked directly on the skin using a non-toxic skin marker. Four sampling sites will be numbered within each abdominal test area, on each side of the abdominal region. The positioning and numbering of the abdominal sampling sites are standard for all subjects. Sampling sites on the contra-lateral side of the abdomen will be numbered in a mirror-image orientation. The four sampling sites within each abdominal test area represent one baseline (pre-prep) site, one post-prep sampling site for each of two sampling times (30 seconds and 6 hours), and one unused sampling site.

Prior to performing the Treatment Day baseline sample collection, a skin irritation assessment will be performed.

If an irritation score of 1 for any individual skin condition at the Treatment Day baseline is assigned, the subject will be excluded from the treatment phase of the study. After abdominal test areas are marked and sample sites numbered, baseline samples will be collected from the appropriate site per the Randomization Scheme in each test area using the scrub cup technique.

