14.4 Randomization Scheme Example

Abdo	minal and Gro	in Sites Bilate	eral Samplir	ng Procedure	Configuration	ons	
		G	ROUP 1				
Key: A =	ZuraPrep™						
-			/ti	t 1\			
	ChloraPrep®			control)			
C =	ZuraPrep™	Vehi	cle (negative	control)			
Subject	Left Treatment	Right Treatment	Site 1	Site 2	Site 3	Site 4	
1001				l			
1002							
1003							
1004							
1005							
1006							
1007							
1008							
1009			Subjects w	vill be numbered	l seguentially f	rom 1001 to	
1010	Treatment		the numl	ber of subjects	treated during	the study.	
1011	block 1		Randomiz	zation will be pe		oup issued	
1012				prior to stud	dy initiation.	1.	
1013							
1014							
1015							
1016				0			
1017				Sample or	der group 1		
1018	Treatment						
1019	block 2						
1020							
1021							
1022							
1023							
1024							
		1					

Page 39 of 53 Zurex Pharma, Inc. Project: ZX-ZP-0092 Microbac Protocol: 865.1.03.25.18

Microbac Project: 865-107

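### Nothing conceals the left/right product assignment from the staff who take the Treatment Day baseline; releasing it only after baseline sampling would be a cheap improvement

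*Combined protocol and SAP*

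**What the plan says.** Section 3.3 makes application and sampling open: "The study materials will not be blinded from the Investigator or other study staff performing the study material application or bacterial sample collections". Blinding is confined to the laboratory count: "The staff member(s) performing bacterial enumeration will be blinded from the identification of treatment assignment".

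On Treatment Day, Section 5.1.2.1.1 (and 5.1.2.1.2 for the groin) has irritation scored first, and then "baseline samples will be collected from the appropriate site per the Randomization Scheme in each test area using the scrub cup technique". Section 5.1.2 says that this same Scheme fixes the product for each side. The example in Appendix 14.4 has a "Left Treatment" column and its right-hand counterpart in the same subject row as Sites 1 to 4. Under Section 5.1.2.2, product goes on only after the baseline sample.

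The baseline then does three jobs:

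- **Evaluability.** Section 3.2: "A site is considered evaluable for efficacy (part of the per-protocol data set) if the criteria in the following table are met". Section 8.1 repeats that "the per-protocol data set will be defined as those sites passing treatment day baselines on a site-by-site basis".
- **Covariate.** The 30-second count is regressed "on the additive effect of a treatment indicator and the baseline or pre-treatment measurements" (Section 3.2; likewise 6.1 and 8.2.1).
- **Comparator.** Persistence at 6 hours is judged against each site's baseline, with a target of 95% to 100% of sites (Sections 3.2.1, 6.1.1 and 8.2.1).

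**The concern.** Once a product is on the skin, open sampling may be hard to avoid. Before application nothing on the skin identifies the product, and the baseline step does not need the assignment. Yet no section withholds it until that step is complete.

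The sample is taken by hand, with a rubber policeman at moderate pressure (Section 5.2.1), so recovery depends partly on the operator. Chance variation in scrubbing, or a habitual left/right difference, is handled by the randomization and the left/right balance. A difference that follows knowledge of the product is not. Each subject carries two products on opposite sides, so such a difference becomes a treatment difference.

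A baseline read high on ZuraPrep sides would favour ZuraPrep in the adjusted 30-second comparison and in the 6-hour percentage; one read low would do the opposite. Counting plates blind cannot undo this, because the error is already in the sample. The pre-baseline irritation score, where a 1 excludes the subject, is a judgement made under the same conditions.

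**Working it through.** **1. Can the assignment be known at baseline?** The final schedule exists before the first treatment, and the sequential subject number covers Treatment Day baseline collection (Section 3.3). The sampler must consult the Scheme for the site (5.1.2.1), and the Scheme holds the product for each side (5.1.2; layout in 14.4). So it can be known, and nothing prevents it. No section says expressly that the sampler has read it by then.

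**2. The plan's own figures.** The balance reproduces: 108 subjects × 2 sides ÷ 3 products = 72 readings per product per region, and 108 ÷ 12 = 9 blocks. The 65 subjects per treatment in Section 8.3 cannot be reproduced, because the effect sizes and SDs are blacked out. I use it only to back-solve an SD, assuming that the non-inferiority comparison drives it, a true difference of 0, one-sided 0.025 and 80% power:

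SD = 0.5 ÷ [(1.960 + 0.842) × √(2/65)] ≈ 1.02

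With 72 readings per product, treated as independent, SE = 1.017 × √(2/72) ≈ 0.17. An SE of 0.15 is shown as a second assumption.

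**3. Effect on the adjusted difference.** If the ZuraPrep baseline is inflated by d and the covariate slope is b, the difference moves by about −b × d. A simulated regression applying the groin limits of Table 3.2 agreed: with b = 0.5 and d = 0.2 it gave −0.104, against −0.10 from the formula.

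**4. Effect on false non-inferiority.** At a true difference of 0.5, the chance of declaring non-inferiority is Φ(b × d ÷ SE − 1.96), which is 2.5% when d = 0.

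| Slope b | Shift d | b × d | SE 0.17 | SE 0.15 |
|---|---|---|---|---|
| 0.3 | 0.1 | 0.03 | 3.7% | 3.9% |
| 0.5 | 0.2 | 0.10 | 8.5% | 9.8% |
| 0.8 | 0.3 | 0.24 | 29% | 36% |

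**5. Effect on persistence.** At 72 sites, 95% means at least 69 (0.95 × 72 = 68.4). If 90% of sites truly meet the criterion, the chance of reaching 69 is 6.2%. With d = 0.2 the apparent rate is Φ(1.282 + 0.2/SD). An SD of the 6-hour change of 1.0 gives 93.1% of sites and a 26% chance of passing; an SD of 0.7 gives 94.2% and 39%.

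**6. Effect on evaluability.** With an assumed groin mean of 5.8 and SD of 0.6 log10, d = 0.2 raises qualifying sites from 91% to 95% on that side only.

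**7. What concealment would leave.** Three products on two sides give 3 × 2 = 6 ordered pairs; assume that each block of 12 holds every pair twice. Staff who have seen the block's earlier assignments would then guess the next pair correctly about 36% of the time, against 17% by chance, and be certain of about 9%.

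**The case against.** A reader might infer that samplers do know the product when they scrub the baseline. The documents do not go that far. Section 3.3 does not say when on Treatment Day the assignment is disclosed. Appendix 14.4 is an example, and Sections 3.3 and 5.1.2 leave further detail to a separate randomization document. The supportable statement is that nothing in the protocol conceals it.

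Several features limit the scope for bias:

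- The baseline site is pre-assigned, and the scrub is timed at one minute, repeated and pooled.
- Plates incubate for 72 ± 4 hours, so the sampler cannot steer a count towards a Table 3.2 limit.
- Both sides have already passed the same minimum at screening, before randomization.
- An inflated baseline can also breach the upper limit and lose the site.
- An irritation score of 1 removes the whole subject, so it cannot drop one product's side alone.

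These points stand. They narrow the problem but do not close it, since hand pressure remains with the operator.

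It is also fair that the larger exposure is the open sampling at 30 seconds and 6 hours. Error in the 30-second count enters the outcome in full, not scaled by a slope. That limits what this change achieves, but it is no reason to leave the baseline unprotected when the baseline can be concealed so easily.

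Finally, treatment and sample order are not wholly unlinked. Section 3.3 has "Sample order will be randomized separately in blocks of 24 based on the 24 possible sample orders", but goes on to match 12 of those orders to the 12 treatment assignments. The matching rule is not given, so a site list cannot be presumed uninformative about treatment.

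**Conclusion.** The point holds as a gap in concealment at the baseline step, on a measurement that bears on every efficacy conclusion. It is a cheap improvement to a declared open procedure. It is not evidence that bias has occurred or would favour ZuraPrep.

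Size and direction cannot be obtained from the documents. Every percentage above rests on an assumed slope, shift and SE. The top of the range needs a 0.3 log10 shift, a systematic twofold difference in recovery (10^0.3 ≈ 2.0), which nothing in the plan supports. The middle case shows only that a modest shift would matter against a 0.5 margin.

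A reader might also infer that hiding the treatment columns would remove the bias at no cost. It would not. Blocks of 12 stay partly predictable to staff who saw earlier applications. Section 4 has replacements treated in the same way as the subjects they replace, so their assignment is known to anyone who knows whom they replace. There is also some handling cost. Most foreknowledge at baseline would go, not all of it.

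**What to change.** Amend Sections 3.3, 5.1.2.1 and 14.4 as follows:

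1. Split the schedule. The sampler receives a site-order sheet (Sites 1 to 4 only) at the start of Treatment Day.
2. Keep the left/right assignment sealed or system-held. Release it, with the time recorded, only after Treatment Day eligibility, the pre-baseline irritation scores and all four baseline samples are recorded.
3. Withhold replacement subjects' assignments from the samplers until the same moment.
4. Confirm in the randomization document that the matching of sample orders to treatments does not let the site-order sheet reveal the product.

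The cost is a paragraph of protocol wording, a two-part schedule, and pre-application weighing of applicators (Section 5.1.2.2) done after baseline or out of the sampler's view. No staff, visits or samples are added, and N (108 subjects, 72 readings per product per region), the analysis and the treatments stay as planned.
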